Patients' baseline characteristics will be summarized according to the two groups. All data will be presented as mean \pm SD or median (interquartile range) for continuous variables, and number (percentage) for categorical variables. Chi-squared or Fisher's exact test (categorical variables) and Student's t-test or Mann-Whitney test (continuous variables) will be used to compare patients between PFPT and written education group at baseline. Paired t-test or Wilcoxon signed-rank test will be used to compare questionnaire scores between baseline and the follow-ups within each group. Student's t-test or Mann-Whitney test will be used to compare the paired difference between the two groups. The Shapiro-Wilk test will be used to check the normality. Pearson's correlation coefficient or Spearman's rank correlation coefficient will be used to analyze the relationships among variables. All analyses will be performed with STATA version 16 (StataCorp. 2019. Stata Statistical Software: Release 16. College Station, TX: StataCorp LLC). Statistical significance will be defined as two-tailed $p < 0.05$ for all tests.

Sample Size Calculation:

Our primary objective of the proposed study is to evaluate the hypothesis that patients attending an educational workshop from PFPTs will have improved knowledge of pelvic floor disorders (PFDs) as measured by the Prolapse and Incontinence Knowledge Questionnaire (PIKQ) as compared to patients in the written education group. We will use the 24-point PIKQ questionnaire composite score as our primary endpoint. Based on the PIKQ validation study, a composite score of 0.45 (45%) is expected in women of this age at baseline.⁸ Assuming in our study population at baseline a score of 0.45, we would expect an increase in the composite

score to 0.8 in the PFPT group and an increase in composite score to 0.54 in the written education group. Therefore, a sample size of 96 patients will be needed to detect the difference with 80% power and a significance level of 0.05 based on the two-sided Z-test with pooled variance. After considering 20% dropout rate from the study, the total sample size will be 120 patients (60 per group). PASS 2015 (PASS 15 Power Analysis and Sample Size Software (2017). NCSS, LLC. Kaysville, Utah, USA, ncss.com/software/pass) was used for sample size calculation.

Study Timeline:

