Patients randomized into the written education group will only receive written materials. They will receive these materials at the first study visit and again when leaving the hospital after delivery. The written materials will consist of three one-page handouts with information on pelvic organ prolapse (POP), stress urinary incontinence (SUI), and pelvic floor exercises. These handouts will be created in collaboration with [name] and [name] who have experience in the study of patient's perceptions of PFDs and have collaborated with the American Urogynecology Society to create written educational materials in the past.⁴ We plan to seek feedback from patients regarding their impressions of our newly developed handouts prior to use.

The PFPT workshop group will both receive the written handouts and attend an in-person education workshop that will be led by a PFPT with approximately 5-10 study participants in each workshop. Patients will be allowed to attend the workshop after being randomized during pregnancy or during the postpartum period to maximize participation. The session will last approximately 1 hour and will review similar information to the content of the handouts. It will focus on educating the patients about pelvic floor anatomy, etiology of PFDs, prevention strategies, and informing them about urogynecologists and PFPTs. The educational workshops will be offered in either in person or virtual format to accommodate group gathering restrictions of COVID-19. The web-based meeting will be password protected and participants will have the option to share their video and do not have to provide their name as the participant if they do not want to. They have the option to verbally participate but this is not required.

Patients will be reassessed and complete the PIKQ and PFDI-20 questionnaires at their 6-week postpartum visit. We will also record delivery type. If patients do not attend their postpartum visit, they will be reached by phone or e-mail to complete the postpartum assessment. Referral patterns to PFPT and urogynecology will be assessed using electronic medical records during the study period and up to 3 months postpartum.

Patients from the workshop group will receive a follow up phone call to perform a brief phone survey on their perceptions of the two forms of educational materials: written versus workshop format. No medical information will be discussed in this phone call. Please see interview guide attached in appendix ***.

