Patient demographic data will be collected from the medical record and the PIKQ survey, including age, race, obstetrics history, marital status, household income, and education level. Delivery type will also be recorded at the 6 weeks postpartum visit. The patients will be asked to give responses to the PIKQ and PFDI-20 surveys. Data collected in the study will include referral patterns within the OBGYN group at Methodist to the urogynecology group and pelvic floor physical therapy group. The referral information will be collected for the 6 months

preceding the study and compared to the data collected during the study period. This data will be recorded on recruitment paperwork with a de-identified subject ID and recorded into a RedCap database.

10. Study Population

We will recruit female patients in the first or second trimester of pregnancy who are 18 years of age or older.

11. Screening and Recruitment^{SR}

Patients will be identified by reviewing the clinical schedule of the general obstetrics providers at Houston Methodist Hospital. The patients will be approached either in the waiting room prior to their appointment or while they are awaiting their physician visit in the clinic room. Patients may also be approached by phone after their visit with a physician if they are attending virtual visits. Recruitment flyers will be posted around the clinical area and waiting room of the Smith 2221 OBGYN clinical area.

12. Withdrawal of Subjects

Subjects may withdraw from the study at any time with no change to their routine obstetric care. Patients who experience a miscarriage or intrauterine fetal demise prior to viability will be withdrawn from participation.

13. Provisions to Protect the Privacy Interests of Subjects

Subjects will be required to provide minimal demographic information at their recruiting visit and this will not need to be repeated at any point. Their primary interaction with the research study team will be at recruitment, at the PFPT group workshop, and at their postpartum visit for the follow up questionnaire administration. The educational workshop will include females only and female PFPTs in small groups of 5-10 subjects. We plan to offer the workshops in either an in-person or virtual format to accommodate for current group gathering constraints due to COVID-19.

14. Risks to Subjects

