There are minimal risks associated with this study. The cost of parking in the medical center may pose a burden to some subjects and so we plan to compensate the cost of parking to try to offset this. Otherwise, there is no physical, social, legal, or psychological risk to the subjects.

15. Potential Benefits

Regardless of the group to which the subjects are randomized, they will be given education on PFDs that they would not typically receive in their routine obstetric care. This may provide the opportunity to make subjects aware of treatment options for PFDs that they were not aware of and provide them an opportunity to improve their quality of life.

A potential challenge would be ensuring that patients receive their follow up assessment as patients may not show up for their postpartum visit. A strategy to improve follow up would be to consent patients to the option of receiving and completing the PIKQ and PFDI-20 by e-mail if they do not attend their postpartum visit. Another potential challenge may be ensuring that patients attend their assigned group workshop. A strategy to improve attendance and

enrollment would be to compensate patients. We plan to compensate their parking on the dates that they attend the group workshop.

16. Financial and Economic Issues

The only cost to the study subjects will be the cost of parking to attend the group workshop. The remainder of the study visits will occur at the same time as routine care visits. We will plan to compensate the cost of parking at the time of their group workshop with an estimated cost of \$960 (\$16 per participant).

17. Data Safety Plan

Please see above description of Data and Specimen Banking.

18. Informed Consent Documentation and Process

Informed consent will be obtained prior to any of the study procedures with the attached informed consent template. Consent will be obtained from a member of the research team. The consent document may be e-mailed to participants after being recruited by phone for their review. They will then sign the consent form at their next in-person physician visit.

19. Waiver of Informed Consent and /or Authorization

A screening waiver will be requested preparatory for research (waiver requested for feasibility, recruiting, access to charts, pre-screening). We are not requesting a waiver of informed consent.

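### Referral, a secondary outcome of a randomised trial, is compared only before versus during the study, with no between-arm analysis and no denominator

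*Combined protocol and SAP*

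**What the plan says.** - **Aim (Section 2).** A secondary aim asks whether written education or the workshop raises referral rates to pelvic floor physical therapy (PFPT) or urogynecology. It names both arms but states no contrast and does not define the rate.
- **Ascertainment (Section 5).** "Referral patterns to PFPT and urogynecology will be assessed using electronic medical records during the study period and up to 3 months postpartum". No comparison is given there.
- **Comparison (Section 9).** Referral information is to be collected for the six months "preceding the study and compared to the data collected during the study period". This is the only referral comparison in the document.
- **Population (Section 9).** The data are described as "referral patterns within the OBGYN group at Methodist to the urogynecology group and pelvic floor physical therapy group", which reads as practice-wide. The same paragraph continues: "This data will be recorded on recruitment paperwork with a de-identified subject ID and recorded into a RedCap database", which reads as participant-level.
- **Tests (Section 4, Statistical Analysis).** The categorical tests, chi-squared or Fisher's exact, "will be used to compare patients between PFPT and written education group at baseline". For follow-up, "Student's t-test or Mann-Whitney test will be used to compare the paired difference between the two groups".
- **Arms.** "The PFPT workshop group will both receive the written handouts and attend an in-person education workshop" (Section 5). Section 15 says of participants in either group that "they will be given education on PFDs that they would not typically receive in their routine obstetric care".

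**The concern.** The trial randomises women to two educational tools, but the one comparison written for referral does not use the randomisation. Any difference between the six earlier months and the study period mixes the effect of education with whatever else changed over time. The protocol itself describes changes in how care was delivered: COVID-19 gathering limits and virtual visits.

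Two further gaps make the result hard to interpret. The outcome is called a rate in the aim and a pattern elsewhere, with no denominator. The two periods may also be counted in different populations, because women seen before the study hold no subject ID. Finally, both arms receive education, so the trial has no randomised group without it, and the plan does not say so. A rise in referrals could be read as an effect of education that the design cannot support, while the one protected comparison is left unspecified or chosen after the data are seen.

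**Working it through.** **1. Is a between-arm referral test stated anywhere?** Going through the Statistical Analysis text in Section 4:

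| Method | Stated use | Covers referral by arm? |
|---|---|---|
| Chi-squared / Fisher's exact | Arms at baseline | No |
| Paired t / Wilcoxon signed-rank | Questionnaire scores within group | No |
| t-test / Mann-Whitney at follow-up | Paired difference between groups | No; no baseline referral value per woman is defined from which to form a difference |
| Correlation coefficients | Relationships among variables | No arm contrast |

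The plan gives no referral rate, effect size or power, so there is no figure of its own to reproduce.

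**2. What calendar drift could do (illustration).** Inputs from the Study Timeline: about 75 obstetric patients per month, and chart rows from July 2020 to August 2021 (14 months). If 75 is taken as the monthly denominator, there are 6 × 75 = 450 before the study and 14 × 75 = 1,050 during it, or 120 if only participants count. The rates are assumed: 5% before and 8% during, with no education effect. The probability of a significant two-sided result is Φ[(|d| − 1.96·s0)/s1], with s0 the pooled and s1 the unpooled standard error.

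- 450 vs 1,050: s0 = 0.01447, s1 = 0.01325; (0.03 − 0.02836)/0.01325 = 0.12, giving about 55%.
- 450 vs 120: s0 = 0.02368, s1 = 0.02681; (0.03 − 0.04642)/0.02681 = −0.61, giving about 27%.

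The nominal level is 5%.

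**3. Only if raw counts were compared.** The study period is not defined. The chart gives 14/6 = 2.33. Six months of recruitment plus about nine months of follow-up gives 15/6 = 2.50. A constant rate would therefore show a 2.3- to 2.5-fold rise.

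**4. What a between-arm analysis could show.** Inputs: 60 per arm and two-sided 0.05 (Section 4). Written-arm rates are assumed, because the documents give none. Chi-squared power uses the formula above, adding the negligible opposite tail. For 10% vs 20%: s0 = √(2 × 0.15 × 0.85/60) = 0.0652, s1 = √((0.09 + 0.16)/60) = 0.0645, and (0.10 − 0.1278)/0.0645 = −0.43, giving 0.33. Fisher power sums both binomial distributions over all tables with p ≤ 0.05. The 95% CI half-width is 1.96·√[(p1(1−p1) + p2(1−p2))/60].

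| Written arm | Workshop arm (doubling) | Chi-squared power | Fisher power | CI half-width | Workshop rate for 80% power (chi-squared) |
|---|---|---|---|---|---|
| 5% | 10% | 0.179 | 0.088 | 0.094 | 22.4% |
| 10% | 20% | 0.334 | 0.247 | 0.127 | 30.3% |
| 20% | 40% | 0.670 | 0.600 | 0.160 | 43.6% |

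With 48 evaluable per arm (the plan's 20% dropout), chi-squared power falls to about 0.15, 0.28 and 0.57.

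**The case against.** The strongest defence is that the historical comparator fits one reading of the aim. If the question is whether any education raises referral, both arms are exposed and a pre-study period is the only comparator available. That explains the choice, but it does not remove the confounding, and the plan does not state the limitation.

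It can also be said that a by-arm comparison is natural in a trial of two tools, with follow-up to three months postpartum and data held under a subject ID. This is fair as far as it goes: the comparison is unspecified, not ruled out. But the only categorical test is confined to baseline, and the only referral contrast actually written is a different one.

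The COVID-19 example has limits. The virtual workshop was added on 7/1/20 and the timeline chart starts that month, so part of the earlier window may also have been affected. The documents do not say when care changed. This stands, and it is why no size or direction is claimed for the bias. A before/after contrast remains inseparable from calendar time whatever the cause.

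Finally, the proposed replacement has low power and answers only part of the aim. Both points are true. An imprecise randomised estimate reported with its interval is still the better main analysis, and the before/after figures can be reported beside it with a clear label.

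**Conclusion.** The concern holds. Following the plan as written gives a non-randomised before/after answer to a secondary aim of a randomised trial, with no denominator and an unsettled population. Even as a rate, the difference could not be attributed to education.

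The bias in the stated comparison cannot be quantified from the documents. The drift figures and the 2.3- to 2.5-fold ratio are conditional illustrations. If counts are practice-wide, any effect among participants would also be diluted by an unknown amount. The power figures describe the replacement analysis under assumed rates of 5% to 20%, and show that it would reliably detect only large differences.

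This should be corrected, but it concerns one secondary outcome. The primary knowledge comparison and its sample size are not affected.

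**What to change.** In Section 4, Statistical Analysis, add as the main referral analysis:

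- the proportion of randomised participants with at least one PFPT or urogynecology referral from randomisation to three months postpartum, by assigned arm;
- the risk difference with 95% CI, and a chi-squared or Fisher's exact test;
- a rule for counting withdrawn participants, since Section 12 withdraws women after pregnancy loss before viability;
- a statement that this tests workshop plus handouts against handouts alone, is imprecise, and that a null result is not evidence of no difference.

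In Section 9, keep the before/after comparison as descriptive only. Express it as referrals per obstetric patient or patient-month, with the same population and referral definition in both periods, and define the study period. State that education versus no education has no randomised comparator and that no causal claim will be made from it.

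**Cost.** The between-arm part needs wording only, provided referrals are captured per participant, as the subject-ID recording indicates; the text should confirm this. The descriptive part needs a denominator for both periods. If that requires records of non-participants, check it against Section 19, which requests only a screening waiver. The price is low power for the randomised contrast and a descriptive answer only on education versus none.

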Appendix A:

Pelvic Floor Disability Index (PFDI-20)

Instructions: Please answer all of the questions in the following survey. These questions will ask you if you have certain bowel, bladder, or pelvic symptoms and, if you do, how much they bother you. Answer these by circling the appropriate number. While answering these questions, please consider your symptoms over the last 3 months. The PFDI-20 has 20 items and 3 scales of your symptoms. All items use the following format with a response scale from 0 to 4.

Pelvic Organ prolapse Distress Inventory 6 (POPDI-6)

Do You...	NO	YES
1. Usually experience pressure in the lower abdomen?	0	1 2 3 4
2. Usually experience heaviness or dullness in the pelvic area?	0	1 2 3 4
3. Usually have a bulge or something falling out that you can see or feel in your vaginal area?	0	1 2 3 4
4. Ever have to push on the vagina or around the rectum to have or complete a bowel movement?	0	1 2 3 4

5. Usually experience a feeling of incomplete bladder emptying?	0	1 2 3 4
6. Ever have to push up on a bulge in the vaginal area with your fingers to start or complete urination?	0	1 2 3 4
	0	1 2 3 4

Colorectal-Anal Distress Inventory 8 (CRAD-8) Do You... NO YES

Do You...	NO	YES
7. Feel you need to strain too hard to have a bowel movement?	0	1 2 3 4
8. Feel you have not completely emptied your bowels at the end of a bowel movement?	0	1 2 3 4
9. Usually lose stool beyond your control if your stool is well formed?	0	1 2 3 4
10. Usually lose stool beyond your control if your stool is loose?	0	1 2 3 4
11. Usually lose gas from the rectum beyond your control?	0	1 2 3 4
12. Usually have pain when you pass your stool?	0	1 2 3 4
13. Experience a strong sense of urgency and have to rush to the bathroom to have a bowel movement?	0	1 2 3 4
14. Does part of your bowel ever pass through the rectum and bulge outside during or after a bowel movement?		

Urinary Distress Inventory 6 (UDI-6) Do You... NO YES

Do You...	NO	YES
15. Usually experience frequent urination?	0	1 2 3 4
16. Usually experience urine leakage associated with a feeling of urgency, that is, a strong sensation of needing to go to the bathroom?	0	1 2 3 4
17. Usually experience urine leakage related to coughing, sneezing or laughing?	0	1 2 3 4
18. Usually experience small amounts of urine leakage (that is, drops)?	0	1 2 3 4
19. Usually experience difficulty emptying your bladder?	0	1 2 3 4
20. Usually experience pain or discomfort in the lower abdomen or genital region?	0	1 2 3 4

Scoring the PFDI-20 Scale Scores: Obtain the mean value of all of the answered items within the corresponding scale (possible value 0 to 4) and then multiply by 25 to obtain the scale score (range 0 to 100). Missing items are dealt with by using the mean from answered items only.

PFSI-20 Summary Score: Add the scores from the 3 scales together to obtain the summary score (range 0 to 300).

Prolapse and Incontinence Knowledge Quiz (PIKQ)

1. In what year were you born? _____
2. How many children have you given birth to? _____
3. Which describes you?

Still have regular periods Near menopause Menopausal

4. Do you work in a medical field?

No Yes (If yes, what do you do? _____)

5. Are you currently married?

No Yes

6. What is your yearly household income?

< \$10,000 \$10,000 - \$49,999 \$50,000 - \$100,000 >
\$100,000

7. What is your highest level of education?

8th grade or less High School College Graduate School

8. Have you ever seen a urologist or urogynecologist for any type of medical issue or problem?

No Yes

9. Have you ever had a problem with urine leakage?

No Yes

10. Have you ever had a problem with pelvic organ prolapse (bulging of the vagina, uterus, bladder, and/or rectum)?

No Yes

11. Have you ever been treated for pelvic organ prolapse (bulging of the vagina, uterus, bladder, and/or rectum)?

No Yes

12. Have you ever been treated for leakage of urine?

No Yes

13. What is your race?

Hispanic White (not Hispanic) African American Asian
Other

Below are some statements about urinary incontinence (loss of urine or leaky bladder). Please state if you agree or disagree with each statement, or if you do not know.

Below are some statements about pelvic organ prolapse (bulging of the vagina, uterus, bladder, or rectum). Please state if you agree or disagree with each statement, or if you do not know.

AGREE	DISAGREE	DON'T KNOW
3. Pelvic organ prolapse can happen at any age.		
AGREE	DISAGREE	DON'T KNOW
4. Certain exercises can help to stop pelvic organ prolapse from getting worse.		
AGREE	DISAGREE	DON'T KNOW
5. Symptoms of pelvic organ prolapse may include pelvic heaviness and/or pressure.		
AGREE	DISAGREE	DON'T KNOW
6. A good way for a doctor to diagnose pelvic organ prolapse is by examining the patient.		
AGREE	DISAGREE	DON'T KNOW
7. Once a patient has pelvic organ prolapse, not much can be done to help her.		
AGREE	DISAGREE	DON'T KNOW
8. Heavy lifting on a daily basis can lead to pelvic organ prolapse.		
AGREE	DISAGREE	DON'T KNOW
